10 EFFICACY ASSESSMENTS

10.1 Health Status using the 7-point Ordinal Scale

This is the main efficacy variable of the study. It will be assessed post-randomization daily in hospital as listed in the Schedule of Events, page 11, and on Day 14 (or assessed upon discharge if discharged earlier than Day 14), and at each of the outpatient contacts (once every 3 days up to Day 29, and on Days 45 and 60). The ordinal scale is an assessment of the health status on a given study day, identifying the worst health status during the previous day of observation. Each day, according to local practice in terms of time of assessment, the worst health status gets scored on the Ordinal scale for the previous day and the score will be recorded. i.e. on Day 5, the worst Day 4 health status is scored and recorded as Day 4 score in the CRF. The scale is as follows and further details on each of the categories 1-6 are presented in 7.1.1.

- 1. Not hospitalized, no limitations on activities
- 2. Not hospitalized, limitation on activities;
- 3. Hospitalized (under observation/admitted), not requiring supplemental oxygen;
- 4. Hospitalized (under observation/admitted), requiring supplemental oxygen at ≤4 L/min³;
- 5. Hospitalized, on non-invasive ventilation or high flow oxygen supplementation at >4 L/min;
- 6. Hospitalized, on invasive mechanical ventilation or ECMO (extra-corporeal membrane oxygenation);
- 7. Death.

3

³ Patients receiving up to 6L/min with a low-flow device can also qualify as an Ordinal Scale "4" if they have a pre-existing health condition (COPD, heart failure, for example) that causes higher oxygen supplementation needs and if the Investigator judges that the patient is NOT in respiratory failure. Other patients are subject to the ≤4L/min threshold.

10.2 Body height, weight, with BMI calculated

Height (screening only) and weight will be measured (can also be self-reported) with shoes off at time points listed in the Schedule of Events, page 11, specifically at screening and on Day 14 (or earlier discharge from hospital). The body mass index (BMI) will be calculated using standard methods, most likely automatically by the eCRF platform.

10.3 Quality-of-Life evaluations

The patient's Quality of Life (QoL) will be assessed at time points listed in the Schedule of Events, page 11, specifically at screening, on Day 14 (or earlier discharge from hospital), on Days 29 and 45, and also be assessed at a longer-term time point approximately 2 months (Day 60) after randomization. A well characterized and widely used QoL instrument will be used, the EQ-5D-5L (EuroQol 5 dimensions) questionnaire. It is relevant to the condition being treated, the inpatient/outpatient settings, is short to answer and is available in both English and French.

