In subgroups 3 and/or 4 (and the combined 3+4 subgroup as well) LAU-7b plus standard of care showed a 100% reduction in the risk of all-causes death and the risk of progressing to invasive mechanical ventilation by Day 60, when compared to placebo plus standard of care, as well as an improvement in the proportion of patients alive and without respiratory failure at Day 29, a faster recovery and shorter hospitalization.

More specifically, none of the 76 moderately to severely ill COVID-19 patients treated with LAU-7b died or progressed to mechanical ventilation, while 4 patients died (4/72, 5.6%, p=0.053) and 5 progressed to mechanical ventilation (5/72, 6.9%, p=0.025) in the placebo arm. For some endpoints, the positive trend is more evident in subgroup 3 while for others, it is subgroup 4 which shows the higher benefit. Combining them increases the sample size and approaches statistical significance. This is indicative that the combined 3+4 population should be studied further to confirm the results above. This positive signal, in particular the total prevention of the need for mechanical ventilation or mortality in subgroups 3 and 4, was recognized by clinicians as being clinically relevant and worthy of clinical confirmation for this particularly underserved hospitalized population. Avoiding at all costs the progression toward respiratory failure and the need for ICU and invasive mechanical ventilation is a high priority.

The subgroup analysis of critically ill COVID-19 patients didn't show an improvement in the LAU-7b arm over placebo, suggesting that patients already in respiratory failure at baseline may be too severely affected by the disease to benefit from LAU-7b treatment.

Summary:

In conclusion, patients that were not in respiratory failure at baseline (Moderate-to-Severe COVID, Health Status 3 and 4) responded positively to treatment with LAU-7b, supporting further evaluation in this patient subset. Safety was excellent in the overall Safety population and particularly in the Moderate-to-Severe COVID patients.

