- 12. Efficacy: Time to mechanical ventilation, defined here as a move from baseline to category 6 on the ordinal scale patient status, compared between the active and control (placebo) arms of the study.
- 13. Efficacy: Time to death, defined here as a move from baseline to category 7 on the ordinal scale patient status, censored to Day 60 if it happens later than Day 60, compared between the active and control (placebo) arms of the study.
- 14. Efficacy: Duration of hospitalization (days) within the study period Days 1-60, compared between the active and control (placebo) arms of the study.
- 15. Quality-of-Life: The change from baseline to Days 14, 29, 45 and 60 in the score obtained on the EQ-5D-5L survey, a well-documented scoring system that has been widely used and validated as a QoL assessment tool, compared between the active and control (placebo) arms of the study, in patients reaching Days 14, 29, 45 and 60 and able to fill the questionnaire.

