9.2.3 In-Hospital Days

For this study in hospitalized patients with confirmed COVID-19 disease, the hospital stay duration will vary as a function of complications/improvement observed with each given patient, the bed and resources availability, rules and restrictions imposed by Health Authorities (Institution, Governmental...etc.). In order to minimize the burden of this study on the hospital resources, the in-hospital study requirements will piggyback on the SOC, with some exceptions. The overall scheme can be found in the Schedule of Event on page 11. Details are presented below.

1. Pre-Dose on Day 4 only:

If the patient has tolerated the Initial treatment of 3 days, if not done previously, a replenishment will be requested in the IWRS and the Follow-up treatment container (22 capsules) will be retrieved from the pharmacy (where applicable) and stored in the ward's refrigerator.

- 2. On Days 5, 8 and 12 (visits 5, 8 and 12, with a window of +/- 1 day while in hospital), the following assessments will be done:
 - a. Concomitant medication verification, including any supplemental oxygen currently in use;
 - b. Directed physical examination (symptom- and disease-driven);
 - c. From SOC, collect the vital signs including heart rate, respiratory rate, oxygen saturation and body temperature (can be done multiple times during each day as part of SOC, but at a minimum twice);

- d. COVID-19 symptom check (including but not limited to, fever, myalgia, coughing, dyspnea, smell and taste alteration, headache, gastrointestinal disorders...etc.) as per SOC;
- e. SOC laboratory tests including at a minimum, urinalysis (dipstick), hematology and serum chemistry, as per Section 11.2 (the laboratory test can be performed within +/- 1 day from the target visit day);
- f. Health status determination using the 7-point ordinal scale;
- g. Handing study medication for intake during the main meal of the day;
- h. Asking safety-focused open-ended questions:
 - i. How is your health today?
 - ii. How is your vision today?
 - iii. How is your skin today?
- i. Adverse event verification and follow-up on ongoing adverse events.

3. On Day 14 or on the Day of hospital discharge (not a preset visit number), the following assessments will be done:

- a. Concomitant medication verification, including any supplemental oxygen currently in use;

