- b. Directed physical examination (symptom- and disease-driven, will not be repeated if assessment done within 2 days from the discharge day);
- c. Body weight with BMI calculated (measured if possible);
- d. From SOC, collect the vital signs including heart rate, respiratory rate, oxygen saturation and body temperature;
- e. COVID-19 symptom check (including but not limited to, fever, myalgia, coughing, smell and taste alteration, headache, gastrointestinal disorders...etc.) as per SOC;
- f. SOC laboratory tests including at a minimum, urinalysis (dipstick), hematology and serum chemistry (will not be repeated if assessment done within 2 days from the discharge day), as per Section 11.2;
- g. Urine (or serum) pregnancy test if applicable;
- h. Health status determination using the 7-point ordinal scale;
- i. Quality-of-Life questionnaire: EQ-5D-5L questionnaire;
- j. If applicable, dispensing to the patient the remaining study drug treatment with instructions for storage in the home refrigerator, self-administration, and return of unused study drug in a prelabeled envelope;
- k. Asking safety-focused open-ended questions:
 - i. How is your health today?
 - ii. How is your vision today?
 - iii. How is your skin today?
- 1. Adverse event verification and follow-up on ongoing adverse events.

4. On all other Days in Hospital until the day before discharge or before Day 14 (Visit numbers = Day of the study): The following assessments will be done:

- a. From SOC, collect the vital signs including heart rate, respiratory rate, oxygen saturation and body temperature (can be done multiple times during each day as part of SOC, but at a minimum twice);
- b. COVID-19 symptom check (including but not limited to, fever, myalgia, coughing, smell and taste alteration, headache, gastrointestinal disorders...etc.) as per SOC;
- c. Health status determination using the 7-point ordinal scale;
- d. Handing study medication for intake during the main meal of the day;
- e. Adverse event verification and follow-up on ongoing adverse events.

5. Early-Termination Visit

This visit may happen anytime a patient elects to withdraw consent or becomes unable to be followed-up, as detailed in Section 8.3. The following assessments can be performed, sometimes indirectly since the patient may not be able to contribute.

- a. Concomitant medication verification, including any supplemental oxygen currently in use, including the oxygen flow;

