- b. If possible, collect the vital signs including heart rate, respiratory rate, oxygen saturation and body temperature;
- c. Urine (or serum) pregnancy test if applicable;
- d. Adverse event verification and follow-up on ongoing adverse events.

9.2.4 Contacts in hospital after Day 14 or after discharge once every 3 days (±2 days from target) and up to Day 29

(not a preset visit number)

The following assessments will be done, either at the hospital, or by phone or using an electronic platform compatible with mobile phones or tablets.

- e. Concomitant medication verification, including any supplemental oxygen currently in use including the oxygen flow;
- f. COVID-19 symptom check (including but not limited to, fever, myalgia, coughing, smell and taste alteration, headache, gastrointestinal disorders...etc.) as per SOC;
- g. Health status determination using the 7-point ordinal scale;
- h. Verification of the study drug intake and accountability, where applicable;
- i. Asking safety-focused open-ended questions:
 - i. How is your health today?
 - ii. How is your vision today?
 - iii. How is your skin today?
- i. Adverse event verification and follow-up on ongoing adverse events.

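### The EQ-5D-5L score called Day 14 is a discharge-day score for anyone sent home earlier, so the between-arm comparison at that time point is confounded by length of stay

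*Protocol*

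**What the plan says.** **Endpoint.** Protocol Section 7.1.3, item 15 (also in the Synopsis) defines a fixed-day endpoint: "The change from baseline to Days 14, 29, 45 and 60 in the score obtained on the EQ-5D-5L survey", compared between arms "in patients reaching Days 14, 29, 45 and 60 and able to fill the questionnaire".

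**Collection.** Section 10.3 schedules the questionnaire "specifically at screening, on Day 14 (or earlier discharge from hospital), on Days 29 and 45", and again at about two months. Section 9.2.3, item 3 describes one visit: "On Day 14 or on the Day of hospital discharge (not a preset visit number), the following assessments will be done". Its list includes "Quality-of-Life questionnaire: EQ-5D-5L questionnaire".

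**After discharge.** Section 9.2.4 covers "Contacts in hospital after Day 14 or after discharge once every 3 days", up to Day 29. Its list has concomitant medication, symptoms, the ordinal scale, drug accountability, safety questions and adverse events, but no EQ-5D-5L. The Schedule of Events agrees: the EQ-5D-5L row is marked at screening, at end of stay or Day 14, at Days 29 and 45, and at Day 60. It is blank in the every-3-days column.

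**Analysis.** Section 12.7.2 specifies an ANCOVA with treatment and the baseline score. It states no term for actual assessment day and no assessment window. The SAP addendum does not mention the EQ-5D-5L; it refers to a full SAP dated 29SEP2023, which is not among the documents.

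**The concern.** Randomization protects a comparison made at the same time in both arms. Here the clock stops at discharge, which happens after randomization and is itself an outcome (duration of hospitalization is endpoint 14).

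The sponsor expects that outcome to differ by arm. Section 5.4.2.1 reports "a faster recovery and shorter hospitalization" on LAU-7b in the pilot patients with Health Status 3 or 4, the population now enrolled. The justification of the primary endpoint, after Section 7.1.2, also anticipates earlier discharge. Section 9.3.5 provides for patients who leave before Day 14 with capsules still to take.

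If the drug works as hoped, the two arms' Day 14 scores are therefore taken on different days of the illness. A null result at the earliest quality-of-life time point could then reflect timing rather than absence of effect.

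**Working it through.** The plan gives no figure for this comparison, so there is nothing to reproduce. The check has a part that follows from the documents and a part that is only illustrative.

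**From the documents.** Let D be the day of discharge. The day on which the so-called Day 14 score is taken is T = min(D, 14).

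- D = 4 gives T = 4, which is 14 − 4 = 10 days early. The next score is at Day 29, 29 − 4 = 25 days later.
- D ≥ 14 gives T = 14, a true Day 14 score.

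No Day 14 score is scheduled for anyone with D < 14, and no analysis rule can recover one.

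**Direction and size (all inputs assumed).** If both arms follow the same score path, then to first order

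bias in the earlier-discharged arm ≈ −(score gain per day) × (gap in mean assessment day).

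With 0.01 to 0.02 index points per day and a gap of 1 to 2 days, this runs from 0.01 × 1 = 0.01 to 0.02 × 2 = 0.04 points of understatement.

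A simulation tests how far this depends on the path. Discharge times are Weibull (shape 1.5), with medians of 5 vs 6, 5 vs 7 and 6 vs 9 days. The score is 0.85 − 0.35 × exp(−k × day), starting at 0.50, with k = 0.03, 0.06 or 0.12. Mean assessment day then differs by 0.9 to 2.1 days. Differences are earlier-discharged arm minus later-discharged arm.

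| Assumed path | True Day 14 difference | Measured | Bias |
|---|---|---|---|
| A. Same rising path in both arms | 0 | −0.008 to −0.033 | −0.008 to −0.033 |
| B. Score recovery faster in proportion to the shorter stay | +0.019 to +0.052 | +0.002 to +0.012 | −0.016 to −0.040 |
| C. Flat scores | 0 | 0 | 0 |
| D. Flat, then a 0.05 drop after going home | −0.003 to −0.010 | 0 | +0.003 to +0.010 |

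Hand check of one cell of A (medians 5 vs 7, k = 0.06): the slope at Day 7 is 0.35 × 0.06 × exp(−0.42) = 0.0138 per day. The gap in mean assessment day is 7.901 − 6.132 = 1.769. The product is 0.024, against 0.023 simulated.

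Within an arm the simulation lets the score depend on the day alone, not on each patient's readiness for discharge. It shows how the sign depends on the path; it does not estimate the bias in this trial.

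**Other time points.** Days 29, 45 and 60 are fixed contacts with windows of ±3 days (Sections 9.2.5 and 9.2.6), and discharge does not move them.

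**The case against.** - **The sign is not known.** No document gives an EQ-5D-5L trajectory, and rows C and D show zero and reversed bias. This stands. Continued improvement is plausible in an acute illness, and ordinal category 2 in Section 7.1.1 describes discharged patients who are still recovering, but it remains an assumption.
- **An earlier day need not be a sicker day.** Discharge follows clinical improvement. Someone sent home on Day 4 is scored when fit to leave, and someone in hospital on Day 14 while still ill enough to stay. This stands too. The fault is that assessment days differ by arm, not that one arm is necessarily scored when sicker.
- **The discharge gap is uncertain.** The pilot finding in Section 5.4.2.1 comes without a figure and from an ad hoc pool of two subgroups. In the overall pilot ITT population the topline secondary endpoints, including duration of hospitalization, showed no significant difference. This limits any statement of size. It does not remove the dependence on discharge, and an earlier discharge is what the trial hypothesizes.
- **The rule is open and narrow.** Section 10.3 states it plainly, Section 9.2.3 explains the wish to spare hospital resources, and one of four time points of one secondary endpoint is affected. All true. Even so, the endpoint definition still promises a Day 14 value.
- **The full SAP may deal with timing.** It could contain a window rule, a sensitivity analysis or a different label. It could not supply scores that were never scheduled.

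**Conclusion.** The timing fault holds. For every patient discharged before Day 14, the value labelled Day 14 is a discharge score, and the stated analysis does not account for this. The comparison at that time point is confounded by length of stay.

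The expected direction is understatement of benefit in the earlier-discharged arm, on condition that scores keep rising between discharge and Day 14. The 0.01 to 0.04 index points come wholly from assumed slopes and stays.

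Three stronger readings are tempting, and the documents do not support them:

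- **That the comparison is certainly biased against LAU-7b.** The sign depends on a trajectory that is not given.
- **That faster recovery would appear as harm.** Where recovery and discharge speed up together (row B), the measured difference shrinks but stays positive. It turns negative only in row A, where the drug changes the discharge date and not the score path.
- **That the quality-of-life objective cannot be answered.** Objective 4 in Section 6 names no day, and Days 29, 45 and 60 remain sound on this point.

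The primary endpoint is not touched.

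**What to change.** **Where collection is still open, or in a later trial.** Add the EQ-5D-5L to the contact nearest Day 14 for patients already discharged, in Section 9.2.4 and the Schedule of Events. Use that score, or the in-hospital Day 14 score, for change to Day 14, and report the discharge score separately. The contact already takes place by phone or electronic platform, so the cost is one short questionnaire and slight patient burden.

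**For the data already collected.** The SAP addendum says results were first released on 14MAR2024, so missing Day 14 scores cannot now be obtained. Keep the pre-specified analysis and:

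1. relabel it *at discharge or Day 14, whichever is earlier*;
2. tabulate the distribution of assessment day by arm;
3. state that it is not to be read as a treatment effect at Day 14;
4. rest the quality-of-life conclusion on Days 29, 45 and 60.

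This costs table and report wording plus one extra table. Removing the Day 14 time point instead would be a change to a pre-specified endpoint after release of results, so relabelling is preferable.

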11 SAFETY ASSESSMENTS

Safety evaluations will include reporting of Adverse Events (AEs), clinical laboratory assessments, and SOC evaluation of vital signs.

11.1 Adverse Events

All AEs will be assessed, documented, and reported in accordance with ICH GCP guidelines.

11.1.1 Documentation of Adverse Events

Adverse events will be collected from the time of informed consent until the End-of-Study follow-up, on Day 60, or until early termination or death, whichever occurs first. An AE is any untoward medical occurrence (which does not necessarily have to have a causal relationship with this treatment). An AE can be any unfavorable and unintended sign (including an abnormal laboratory finding, for example), symptom, or disease temporally associated with the use of an investigational product, whether or not related to the study drug. This includes any occurrence that was new in onset or aggravated in severity or frequency from the screening condition. As the study subjects are hospitalized, planned surgical procedures for an illness or disease that existed before the patient was screened in the study are **not** to be considered AEs.

Abnormal results of diagnostic procedures, including laboratory test abnormalities, are considered AEs if they result in any one of the following:

- Discontinuation of study treatment;
- Require treatment or any other therapeutic intervention;
- The necessity for further diagnostic evaluation (excluding a repetition of the same procedure to confirm the abnormality);
- Association with clinical signs or symptoms that may have a significant clinical impact, as determined by the Investigator.

Patients are encouraged to report AEs spontaneously or in response to general, non-directed questioning. All AEs are to be followed until resolution or until a stable clinical endpoint is reached. The investigator should question patients about AEs and changes in pre-existing illnesses since their last visit and must record the information in the patients' medical records. The onset and end dates, severity, relationship to study agent, action taken, and outcome must be recorded for each AE. All AEs are to be recorded on the appropriate CRF and in detail on the source documents.

Any AE that occurs from the first dose of study treatment (or prior to the first dose of study treatment, and worsening after first dose of study treatment) until the End-of-Study follow-up, on Day 60, or until early termination or death, whichever occurs first, will be considered treatment emergent (TEAE) and must be recorded in the CRF and, if an SAE, reported immediately to the Sponsor. Adverse events that are ongoing at the end of the follow-up period should be marked as ongoing. However, it is the responsibility of the Investigator to follow up on these events until resolution, where possible, according to standard medical care.

Any AE or SAE that the investigator becomes aware of outside of the reporting period until the end of the study participation of a patient that has or is believed to have a causal relationship to the study drug should be reported to Laurent Pharmaceuticals via telephone. Patients who experience AEs will be monitored with relevant clinical assessments and laboratory tests, as determined by the Investigator. All AEs and laboratory abnormalities encountered during the study should be followed until resolution or stabilization of the event(s). Any action taken and follow-up results must be recorded in the patient's medical record. Follow-up laboratory results should be filed with the patient's source documentation and CRF. For all AEs that require the patient to discontinue treatment, relevant clinical assessments and laboratory tests should be performed until final resolution or stabilization of the event(s). These assessments should be captured in the source data and SAE forms but will not be entered in the CRF.

Due to the critical nature of the COVID-19 infection and its expected complications in mechanically ventilated patients, a revised definition of reportable adverse events (AEs) was developed for use following the Canadian guidelines for AE/SAE reporting in academic critical care trials ⁴. The following 2 categories of events will therefore not be reported in the eCRF:

- Any expected adverse complications related to treatments/procedures commonly administered in the context of invasive mechanical ventilation, such as right main bronchus intubation, lacerated lips, tongue, pharynx and trachea, vocal cord injury, chipped teeth, aspiration, introduction of infection, airway obstruction, hypoxia, hypotension, and cardiac arrhythmias.
- Abnormal Laboratory variations considered clinically significant (eg, leukopenia, transaminitis, lymphopenia, leukocytosis, hypokalemia, hyponatremia and elevated inflammatory markers like D-dimer) that could result from COVID related acute care procedures and medications.

All AEs for randomized patients will be recorded in the CRF and the patient's source documents. AEs for patients who are screened but not subsequently randomized in the study will be recorded in the patient's source documents and in the CRF. The following data should be documented for each AE:

- Description of the event;
- Classification of "serious" or "not serious";
- Date of first occurrence and date of resolution (if applicable);

⁴ Cook D, Lauzier F, Rocha MG, Sayles MJ, Finfer S. Serious adverse events in academic critical care research. CMAJ. 2008 Apr 22;178(9):1181-4

- Severity;
- Causal relationship to study drug(s);
- Action taken;
- Outcome;
- Concomitant medication or other treatment given

An independent DSMB will assess AEs that are reported from study sites. The DSMB will meet at regular intervals throughout the duration of the study or will meet as determined by the DSMB chair, and may recommend systematic treatment arm dose reduction or early termination of the study for safety reasons (see Sections 7.2.2 and 7.2.3)

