11.1.1.1 Adverse Event Severity

The Investigator must determine and record the severity of all serious and non-serious AEs. The Common Terminology Criteria for Adverse Events (CTCAE), Version 4.03, (Cancer Therapy Evaluation Program website; available at: http://ctep.cancer.gov/protocolDevelopment/electronic_applications/ctc.htm; accessed 01 December 2015) should be used for grading the severity of AEs. AEs of CTCAE Grades 4 and 5 should be documented as "life-threatening."

The severity of an AE that does not appear in the CTCAE scale should be determined according to the definitions below. Clinically significant laboratory tests should be recorded as AEs in the patient's source documents and e-CRF.

Severity will be assessed according to the following criteria:

Classification	Definition
Mild (Grade 1)	Mild level of discomfort and does not interfere with regular activities
Moderate (Grade 2)	Moderate level of discomfort and significantly interferes with regular activities
Severe (Grade 3)	Significant level of discomfort and prevents regular activities
Life-threatening (Grade 4)	Any adverse drug experience that places the patient, in the view of the investigator, at immediate risk of death

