11.2 Clinical Laboratory Assessments

Blood and urine samples will be collected according to the Schedule of Events (page 11) and analyzed locally at the clinical site's laboratory as per their SOC. Laboratory test results that are abnormal and considered clinically significant must be reported as AEs (as per Section 11.1.1). Screening laboratory results must be available and reviewed by the Investigator before randomization. The typical safety laboratory test panels are shown in Table 2 below (it is acceptable that SOC varies between clinical sites regarding some tests, but testing must include at the minimum tests evaluating the hematologic status, the kidney and the liver functions. The tests marked by a (+) are suggested:

Table 2: Laboratory Tests Panels

Serum Chemistry	Hematology	Urinalysis*	
Albumin+	Hematocrit+	Nitrite	
Creatinine+	Hemoglobin+	Urobilinogen+	
Total protein	Red blood cells+	Protein+	

Potassium Mean corpuscular hemoglobin pH+
Sodium Mean corpuscular hemoglobin Blood+

Calcium Mean corpuscular volume Leucocyte esterase
Bicarbonate Reticulocytes Specific gravity

PhosphatePlatelet count+KetonesAlkaline phosphatase+Leucocytes+Bilirubin+ALT+Differential (absolute and %)Glucose+AST+EosinophilsAppearance

GGT Basophils
Total bilirubin+ Neutrophils+
Blood urea nitrogen+ Lymphocytes+
Glucose Monocytes

For the purpose of this study conduct, the laboratory tests performed in the local laboratory are the primary tests. Normal ranges and accreditations should be current and filed in the Investigator Site File and in the study's Trial Master File.

In addition, according to the Schedule of Events, pregnancy tests (β -human chorionic gonadotropin) for females of childbearing potential: Urine (or serum) samples will be obtained as specified in the Schedule of Events, page 11 and tested. The urine (or serum) pregnancy test pre-randomization must be negative before the first dose of study drug. Finally, clinical laboratory evaluations may be performed at other times if judged to be clinically appropriate by the Investigator.

Reporting requirements for laboratory tests performed to monitor a SAE, in addition to the protocol-requested safety laboratory tests: Patients experiencing a worsening of their condition (generally a life-threatening situation declared as a SAE) are subject to receiving numerous con-meds, spontaneous treatment adjustments, along with frequent safety laboratory testing.

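### Section 11.1.1 keeps some clinically significant laboratory abnormalities out of the eCRF while Section 11.1.1.1 requires them there as AEs, so laboratory-based TEAEs could be under-counted and recorded differently by site

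*Protocol*

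**What the plan says.** Protocol Section 11.1.1 introduces an exemption by pointing to the critical nature of the infection and "its expected complications in mechanically ventilated patients, a revised definition of reportable adverse events (AEs) was developed". It then states: "The following 2 categories of events will therefore not be reported in the eCRF". The first category is complications of procedures used with invasive ventilation. The second is "Abnormal Laboratory variations considered clinically significant (eg, leukopenia, transaminitis, lymphopenia, leukocytosis, hypokalemia, hyponatremia and elevated inflammatory markers like D-dimer", qualified as those "that could result from COVID related acute care procedures and medications".

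Other text on the same subject:

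- Section 11.1.1, directly after the exemption: "All AEs for randomized patients will be recorded in the CRF and the patient's source documents".
- Section 11.1.1, earlier: a laboratory abnormality counts as an AE if it meets any one of four criteria. These include stopping study treatment and needing treatment. No cause is excluded.
- Section 11.1.1.1: "Clinically significant laboratory tests should be recorded as AEs in the patient's source documents and e-CRF".
- Section 11.1.2: a clinically significant worsening of a laboratory test is documented as an AE.
- Section 11.2: "Laboratory test results that are abnormal and considered clinically significant must be reported as AEs (as per Section 11.1.1").

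The SAP addendum does not address the question.

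**The concern.** The same finding, for example a clinically significant transaminase rise in a patient on COVID standard of care, is kept out of the eCRF by one rule and required there by another. Section 12.8.1 builds the TEAE tables, including the table of TEAEs leading to treatment discontinuation, from recorded AEs. Sections 7.2.2 and 11.1.1 have the DSMB review AEs reported by the sites, by organ class. Hepatic and hematologic incidences would then depend partly on which rule a site followed.

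The protocol treats liver findings as important enough for a discontinuation algorithm (Section 11.4). It also describes the pilot safety profile in favorable terms (Section 5.4.2.1). A safety conclusion of that kind needs AE data collected under one rule.

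**Working it through.** This is a comparison of text, with one small count.

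**1. Is there a direct conflict?** Section 11.1.1.1 covers clinically significant laboratory tests, names the e-CRF and states no exception. The exemption in Section 11.1.1 covers a subset of the same tests and removes them from the same database. Both cannot be followed for a test in that subset. Sections 11.1.1 (the four criteria and the sentence that all AEs go in the CRF) and 11.1.2 support the recording side. Section 11.2 is ambiguous: it requires AE reporting but refers back to Section 11.1.1, which holds both the criteria and the exemption.

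**2. Does the qualifier remove the conflict?** It narrows the exemption, so not every clinically significant laboratory result is covered. But all patients receive COVID standard of care (Section 9.3), and whether an abnormality could come from that care is left to the investigator's judgment with no criteria. Section 11.1.1.2 defines a possibly related event as one that may also have another etiology, and counts it as related in summaries. The exemption can therefore remove events that the causality section would have the investigator assess and perhaps count as related.

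**3. Does the scope match the reason given?** The reason concerns ventilated patients. The first category is tied to ventilation; the laboratory category is not. The pilot figures in Section 5.4.2.1 for baseline Health Status 3 or 4, the only group enrolled in the extension, are:

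- LAU-7b: 0 of 76 progressed to mechanical ventilation.
- Placebo: 5 of 72 progressed (6.9%).
- Together: 76 + 72 = 148 patients, 0 + 5 = 5 ventilated.
- Not ventilated: 148 − 5 = 143, and 143 / 148 = 96.6%. In placebo alone, 67 / 72 = 93.1%.

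This is the share of patients to whom the stated reason would not apply but to whom a site could apply the laboratory category as worded. It does not count missed AEs.

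**4. What else captures the signal?** Scheduled laboratory tests at screening, around Days 5, 8 and 12 in hospital, and at discharge or Day 14 are entered and summarized (Schedule of Events; Sections 11.2 and 12.8.2). Section 8.3 requires the reason for drug discontinuation on the CRF. These sources have gaps:

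- Section 12.8.2 plans means, standard deviations, medians and ranges. It has no threshold or shift counts, although Section 12.8.3 specifies them for vital signs.
- Section 11.2 keeps out of the eCRF laboratory tests done to monitor an SAE, and does not require results after intubation.
- Section 11.1.1 keeps out of the CRF the follow-up assessments for AEs that led to discontinuation.
- A discontinuation reason on the CRF does not by itself create a TEAE record.

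A handful of liver or blood-count events could leave little trace in these summaries.

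**The case against.** The strongest reply is that the text can be read narrowly. Both exempt categories follow from one sentence about ventilated patients, and other provisions also reduce data entry after intubation (life-support medications in Section 11.1.3.1, laboratory results in Section 11.2). On that reading few patients are affected, and the general sentence in the severity-grading section lacks only a cross-reference. This is a plausible intention. It is not what the laboratory category says, and a site reading that bullet alone would have no reason to restrict it.

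Four stronger inferences are tempting, and the documents do not support them:

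- **That the rule biases the comparison or conceals a drug effect.** The trial is blinded and randomization is stratified by site (Sections 7.3.2 and 7.3.3), so each site's practice applies to both arms. The supported concern is under-counting, weaker detection and sites that are not comparable.
- **That patients taken off drug for a laboratory change necessarily leave no AE.** Section 11.1.1 already makes such a change an AE, and Section 8.3 records the reason. The entry is missing only if a site lets the exemption override that criterion.
- **That kidney AEs are exempt in the same way.** No renal marker is among the named examples. The list is illustrative, so one could be argued in, but the text does not show it.
- **That Section 11.2 flatly contradicts the exemption.** It defers to Section 11.1.1. The clear conflict is with Section 11.1.1.1.

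**Conclusion.** The recording rules conflict as written, and no section says which one prevails. If sites apply the laboratory exemption literally, it reaches non-ventilated patients, who were 143 of 148 (96.6%) in the relevant pilot group. Laboratory-based TEAEs, including some leading to treatment discontinuation, could then be under-counted in both arms and recorded unevenly across sites. The scheduled laboratory values and discontinuation reasons replace only part of what is lost.

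The effect on AE rates cannot be sized: the documents give neither counts of laboratory AEs nor information on which rule sites followed. The conclusion assumes that at least some sites used the exemption outside ventilated patients; if none did, the practical effect is small. The point concerns safety reporting and does not touch the primary endpoint. It should be corrected.

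**What to change.** For the protocol text:

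- Reconcile Sections 11.1.1, 11.1.1.1, 11.1.2 and 11.2 into one recording rule, with cross-references.
- Limit the laboratory exemption to ventilated patients, in line with its own stated reason.
- State that a laboratory abnormality leading to study drug discontinuation, already an AE under the criteria in Section 11.1.1, is always entered as one.

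For this trial, the SAP addendum (Introduction) says that the database is locked and that results were first released on 14 March 2024, so site recording can no longer be changed prospectively. The CSR should disclose the conflicting rules. It should also reconcile discontinuation reasons and entered laboratory values against recorded TEAEs, by arm, and report any abnormality that led to discontinuation without a matching TEAE.

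The cost is modest extra AE entry under a revised rule, or reconciliation work on data already held. No clinical threshold or stopping criterion changes.
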